***Primary outcomes:***

The accuracy of the algorithm developed with artificial intelligence to predict the “T” staging in esophageal cancer

***Secondary outcomes:***

In addition to the demographic data of the patients, post-treatment mortality, morbidity rates, complication rates.

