## **METHOD-MATERIAL**

### ***Design***

The study, which included patients with histopathological proven diagnosis of esophageal cancer, was designed prospectively between the years 2021-2022. This research is the first pilot study of an ongoing project of artificial intelligence applications in the staging of upper gastrointestinal tract cancers. The study was carried out in 2 different centers, which are 3rd level training and research hospitals.

Approval was obtained from two separate local ethics committees (Van Training and Research Hospital Ethics Committee 26/12/2019, 2019/22 and Van Yuzuncu Yil University Ethics Committee 15.12.2021, 2021/17).

In both centers participating in the study, all cancer patients are evaluated weekly by the oncology council. Tomography images of esophageal or stomach cancers that come to these councils are recorded. During the council, the "T" stage of the tumor is specified and recorded by the radiologist. According to this pre-treatment clinical staging, which is also confirmed by oncology and general surgery specialists, the treatment protocol that the patients will receive is determined.

In this study, tumors were marked on tomography images of patients who were admitted to the council at the time of new diagnosis or after neoadjuvant therapy (Figure-1). After marking, these images were taught to algorithms developed with the technique described in detail below. Thus, algorithm training is completed with these images.

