### ***Duration of study/number of patients***

This study, in which artificial intelligence applications are planned to be developed through tomography images of patients, is planned to last two years. The more data inputs into the study, the better the training of algorithms will be, and the admission of patients will continue throughout the study period. After the last patient is recruited, the final revision of the developed algorithms will be made. The current pilot study was evaluated with data from 50 patients.

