### **Inclusion criteria:**

Each patient meeting the following criteria will be included in the study.

- 1- Being diagnosed with esophageal cancer (adenocarcinoma or squamous cancer) histopathologically
- 2- Being over 18 years old
- 3- Having a tomography image before or after chemotherapy.
- 4- Giving informed consent to participate in the study.
- 5- Having final pathological staging after surgery.

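### Do the mortality, morbidity and complication rates need a stated start, window and denominator before they can be reported?

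*Combined protocol and SAP*

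**What the plan says.** The Secondary outcomes section is one sentence. Besides demographic data, it names "post-treatment mortality, morbidity rates, complication rates". No other section returns to these outcomes: the measurement parameters, the details of the AI classification, the outcome measures and the comparison with pathology deal only with CT images, T stage and accuracy.

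Three other places bear on how the rates could be read.

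- **Duration of study/number of patients.** The study "is planned to last two years" and "the admission of patients will continue throughout the study period". The one step described after that is: "After the last patient is recruited, the final revision of the developed algorithms will be made". Of the pilot it says: "The current pilot study was evaluated with data from 50 patients".
- **Inclusion criteria, item 5.** Patients must meet the condition "Having final pathological staging after surgery".
- **Design.** Images come from "patients who were admitted to the council at the time of new diagnosis or after neoadjuvant therapy". The T stage recorded at council is introduced with the words "According to this pre-treatment clinical staging".

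**The concern.** A mortality or complication rate means little without a start and a window. Here the recruitment plan appears to make the omission matter. If admission runs to the end of a two-year study and nothing is added afterwards, follow-up ranges from almost nothing to at most 24 months. A plain percentage over all patients would then average over very different exposure times. Two cohorts with the same prognosis could show different rates only because one recruited earlier, and a window left open could be picked after the data are seen.

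Two further points look troublesome. Because item 5 requires a surgical pathology stage, the rates can describe only resected patients, and nobody included can have died before surgery. If the clock started before surgery, every included patient would have a stretch in which death is impossible by construction. Its length could differ between patients entered at diagnosis and those entered after neoadjuvant therapy.

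**Working it through.** The plan gives no figure for these outcomes, so there is nothing to reproduce. The check asks how large the distortion could be under each reading of the window.

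**Inputs from the document:** study length T = 24 months; 50 pilot patients (both from Duration of study/number of patients).

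**Assumptions, none in the document:** even recruitment over the 24 months; surgery at entry; data cut at month 24 with no added follow-up; constant hazard; 12-month mortality of 30% (range 20% to 40%); a crude percentage that counts incomplete windows as event-free.

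**Step 1: share of patients with an incomplete window w.** With even recruitment this is w/T.

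- 30 days: 1/24 = 4.2%
- 90 days: 3/24 = 12.5%
- 12 months: 12/24 = 50%

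If recruitment rises linearly the share is 1 − ((T − w)/T)², giving 8%, 23% and 75%. If it falls linearly it is (w/T)², giving 0.2%, 1.6% and 25%. If prognosis does not depend on entry date, this share is also the largest fraction by which the rate can be lowered, whatever the hazard.

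**Step 2: the crude fixed-window rate.** The hazard is h = −ln(0.70)/12 = 0.0297 per month, and F(t) = 1 − exp(−ht). Patients with a complete window contribute F(w). The others contribute the mean of F over 0 to w, which is 1 − F(w)/(hw). At 12 months:

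0.5 × 0.300 + 0.5 × (1 − 0.300/0.3567) = 0.150 + 0.5 × 0.159 = 0.229.

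| Window | True rate | Crude rate | Difference (points) | Relative loss |
|---|---|---|---|---|
| 30 days | 2.93% | 2.87% | 0.06 | about 2% |
| 90 days | 8.53% | 8.01% | 0.52 | about 6% |
| 12 months | 30.0% | 22.9% | 7.1 | about 24% |

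For 12-month mortality of 20% to 40%, the relative losses stay near 2%, 6% and 23–24%.

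**Step 3: an open-ended percentage.** With even recruitment it is 1 − (1 − exp(−24h))/(24h) = 1 − 0.51/0.7133 = 28.5%. Early-loaded recruitment gives 36.9% and late-loaded 20.1%. First-year entrants would show 41.1% and second-year entrants 15.9% with identical prognosis.

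**Step 4: how far the 24 months apply to the 50 patients.** The section states the two-year duration as a plan and the pilot as already evaluated. It does not say that the 50 were recruited over 24 months or that their data were cut at month 24, so converting the shares into counts out of 50 needs a further assumption. With a pilot period of 12 months (assumed) and a cut at its end, the 30-day share is 1/12 = 8.3%. The 2.93% rate could then fall by at most 0.083 × 2.93 = 0.24 points. With 3 months added after a 24-month recruitment, the 30-day and 90-day windows are complete and (12 − 3)/24 = 37.5% of the 12-month windows are not.

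**Step 5: the start of the clock.** The Design section places council staging before treatment, and the secondary outcomes are labelled as coming after it. A clock started at council contradicts that label. A start at neoadjuvant therapy is still possible in principle, and would guarantee survival to surgery. It concerns death only: morbidity and complications before surgery can be observed in included patients.

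**The case for a change.** The strongest case for a change is that it would be cheap. One or two sentences would settle the start and window, they need only dates that any post-operative rate requires, and nothing elsewhere in the document supplies them. Once listed as outcomes, the rates may be published, and a reader could not compare an unlabelled percentage with anything. The calculations show that a 12-month or open-ended figure can be badly off.

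Much of this stands. The treatment is not named, the window and denominator are absent, and the long-window arithmetic is right given its assumptions. However, the large figures need two things that the document does not contain: a long or open-ended window, and a crude percentage that ignores follow-up. The word post-treatment does give a nominal start; what is missing is which treatment. All the event-rate calculations are for mortality, at rates with no source in the document, and say nothing about morbidity or complications. Naming surgery as time zero from outside would also settle a question that belongs to the investigators, and would drop any neoadjuvant complications they meant to count.

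The restriction to resected patients is not a fault in itself. Item 5 supplies the pathological T stage against which the algorithm is judged, and descriptive rates describe the patients enrolled.

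**Conclusion.** The omission is genuine but does not call for a change. It is missing detail that an analyst fills when the table is built, because a mortality or complication count cannot be made without deciding which event, from which date, over which period. The rates sit beside demographic data as description of a pilot cohort, with no hypothesis, comparison or planned analysis attached, and the primary accuracy outcome does not use them.

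The size depends on the reading. All included patients have had surgery, and mortality is listed with morbidity and complications, so an in-hospital or 30-day post-operative rate is a natural reading, though the document does not state it. The loss is then about 2% of the rate, and at most 4.2% whatever the hazard, under even 24-month recruitment with no added follow-up and prognosis unrelated to entry date. A 12-month crude rate would lose 23–24% of its value under the same recruitment with constant hazard and 12-month mortality of 20% to 40%. That would matter if such a rate were reported without regard to follow-up, but the plan does not say that it will be.

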***Tomography shooting technique and drawing technique of images:***

CT examinations were performed with a 128 slice CT [Siemens Definition AS +(Plus) ], Siemens AG, Munich, Germany] device. The acquisition parameters (mAs, Kv, slicethickness) were as follows, respectively: ThoraxCT (110, 120, 3 mm) and abdomen CT (210, 120, 3 mm). CT scans were performed after 12 hours of fasting, and 1500 ml of water was drunk within 60 minutes of all patients before the extraction to distend the esophagus, stomach and intestines. Iokexol (Omnipaque or Opaxol), which is a non-ionic contrast agent, was administered 100 ml with an automatic injector at a rate of 3 ml/s by IV route. In ThoraxCT, imaging was performed from the distal neck to the upper abdomen, and in abdominal CT, from the diaphragm to the

symphysispubis level. All images are available in our PACS system and were evaluated by consensus by two radiologists with 15 and 17 years of thoracoabdominal CT experience. Tumors were also drawn on images by two radiologists. Readers were blind to both the pathology result and the AI prediction result.

***Pathological evaluation:***

The specimens were fixed in 10% formalin solution for 24 hours. Tissue sections taken after routine tissue macroscopic examination embedded in paraffin blocks. Then, from the prepared paraffin blocks, 4 mm thick sections were taken and stained with hematoxylin-eosin (HE). Microscopic examination of the primary tumor in the evaluation. Pathological staging was done according to American Joint Committee on Cancer as TX, T0, Tis, T1(a/b), T2, T3 and T4(a /b [14].

Predicting “T” stage of esophageal and gastric cancers in computed tomography images

**Measurements parameters:**

- 1- Patient’s CT images
- 2- Patient’s pathology “T” stages

### **Details:**

We will collect all CT images, start from cervical region to upper abdomen. Images from DICOM will be converted to JPEG. Then these images will be classified with help of artificial intelligence (AI) algorithms. Training of algorithm will be performed with data previously collected and testing with new patients when available. New patient images will be evaluated for "T" stage by artificial intelligence algorithms. Then these predictions will be compared with pathological results and parameters below will be measured:

- 1- positive prediction value
- 2- false positive value
- 3- accuracy rate
- 4- sensitivity and specificity

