**Comparing AI success to pathology results:**

	PATHOLOGY T 0	PATHOLOGY T 1	PATHOLOGY T 2	PATHOLOGY T 3	PATHOLOGY T 4	TOTAL
AI-T0	A	B	C	D	E	A+B+C+D+E
AI-T1	F	G	H	I	J	F+G+H+I+J
AI-T2	K	L	M	N	O	K+L+M+N+O
AI-T3	P	Q	R	S	T	P+Q+R+S+T
AI-T4	U	V	W	X	Y	U+V+W+X+Y
TOTAL	A+F+K+P+U	B+G+L+Q+V	C+H+M+R+W	D+I+N+S+X	E+J+O+T+Y	A+B+C+...+X+Y

- Sensitivity of AI-T1 =  $\frac{G}{B+G+L+Q+V}$
- Accuracy of AI-T1 =  $\frac{G+(A+M+S+Y)}{A+B+C+\dots+X+Y}$ 
  - for us 5% prediction precision will be important
- Sample size formula =  $\frac{Z_{1-\alpha/2}^2 \times S_N \times (1-S_N)}{L^2 \times Prevalence}$

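### The plan classifies CT images against one pathological T stage per patient, but does not say what the 5x5 table counts or how image outputs become one stage

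*Combined protocol and SAP*

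**What the plan says.** The procedure is in the Details section. Collection is broad: "We will collect all CT images, start from cervical region to upper abdomen". DICOM data are converted to JPEG, and then "Then these images will be classified with help of artificial intelligence (AI) algorithms". Training uses data already collected, with "testing with new patients when available". At test, "New patient images will be evaluated for" T stage. The last step is: "Then these predictions will be compared with pathological results and parameters below will be measured".

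The reference belongs to the patient. The Inclusion criteria require a final pathological stage after surgery, and Measurements parameters sets "Patient’s CT images" (plural) beside the patient's pathological T stage. The Design section says that treatment is chosen from the clinical T stage recorded for the patient.

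The section Comparing AI success to pathology results gives a 5x5 table of AI stage by pathological stage, cells A to Y, with sensitivity and accuracy formulas on those cells. It names no counting unit. It adds "for us 5% prediction precision will be important" and an entry headed "Sample size formula" without values for its terms. The section on study duration and patient numbers says that the pilot used data from 50 patients.

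The Design section promises a detailed description of the algorithm technique further on. The text that follows covers CT acquisition, tumour drawing and pathology, but not whether the algorithm returns a result per slice, per scan or per patient.

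**The concern.** The primary outcome is the accuracy of predicting T stage. T stage is a property of the patient's tumour, so the question is how often a patient is staged correctly. The plan describes predictions on images and has no step from several image outputs to one stage.

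If the table is filled with images, three things follow:

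- A patient with many images counts more than a patient with few.
- The result is a proportion of images, not of patients, correctly staged.
- Images of one patient share a tumour and a reference label, so their errors are likely to be correlated. An interval that treats them as independent is then too narrow.

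If the table is filled with patients, some rule must have turned the image outputs into one stage, unless the algorithm itself returns one stage per patient. A rule chosen after the test results are known can be chosen because it gives the better accuracy.

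**Working it through.** **Step 1: look for the unit and the rule.** Details names images when it describes classification and evaluation, names patients when it describes testing, and names only predictions when it describes the comparison. Conversion to JPEG, a two-dimensional format, points towards separate images. Measurements parameters and the Inclusion criteria fix the reference at patient level. The 5x5 table has placeholder cells and no unit. Nothing in the document supplies a combining rule such as majority vote, highest stage or mean probability.

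**Step 2: the plan's own figure.** The only number is 50 patients. It is not said to come from the sample size formula, whose sensitivity, prevalence and alpha have no values. There is therefore no calculation to reproduce, and what follows is an illustration.

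**Step 3: inputs.**

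- From the documents: 50 patients; 3 mm slice thickness.
- Assumed: true accuracy 80%; 20 tumour-bearing images per patient (60 mm / 3 mm = 20); all 50 patients used for testing; within-patient correlation (ICC) 0.3 to 0.8; two-sided 95% intervals.

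**Step 4: half-width of the interval for overall accuracy.** The formula is 1.96 × √(p(1−p) × DEFF / n), with DEFF = 1 + (m − 1) × ICC and m images per patient.

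- Patients counted once, n = 50: 1.96 × √(0.16/50) = 0.111, or ±11.1 points (±12.7 at 70% accuracy, ±8.3 at 90%).
- Images treated as independent, n = 50 × 20 = 1,000: 1.96 × √(0.16/1,000) = 0.025, or ±2.5 points (±3.5 with 10 images each, ±1.8 with 40).
- The same 1,000 images, ICC 0.3: DEFF = 1 + 19 × 0.3 = 6.7, giving ±6.4 points.
- ICC 0.5: DEFF = 10.5, giving ±8.0 points.
- ICC 0.8: DEFF = 16.2, giving ±10.0 points.

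The naive interval is too narrow by a factor √DEFF: 2.6 at ICC 0.3, 4.0 at ICC 0.8, and √20 = 4.5 if all images of a patient agree.

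**Step 5: fewer test patients.** Details trains on earlier data and tests on new patients, so fewer than 50 may be available for testing. With 20 test patients, 1.96 × √(0.16/20) = 0.175, or ±17.5 points.

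**Step 6: whether the combining rule matters.** In a two-outcome simplification with independent image errors, 70% accuracy per image becomes 84%, 92% or 97% after a majority vote over 5, 11 or 21 images. Independence makes this an extreme case; if all images of a patient agree, voting changes nothing. Between these limits, the reported accuracy depends on a choice that the plan leaves open.

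**The case against.** The strongest reply is that the table was meant for patients all along. The study recruits and counts patients, pairs each patient's images with that patient's pathology, and tests on new patients. A sentence about evaluating a new patient's images can mean that the whole set is read to give one stage. If the algorithm takes a full scan and returns one stage, there is nothing to combine. On this view a one-sentence clarification is enough.

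Much of this stands. The text is ambiguous, and a reader who infers that the plan prescribes an image-level table at every step goes further than the documents allow. But testing on new patients says how training and test data are separated, not what a cell counts. No section says that the output is one stage per scan. A patient-level table still needs either that statement or a rule.

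Two further inferences are tempting and not supported. One is that tumour-free slices carry the patient's T label, because all images are collected; the tumour marking in the Design and tomography sections points the other way. The other is that a patient enters twice, with scans before and after chemotherapy; the criteria allow either scan but do not say that both are used.

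It is also fair that the magnitudes rest almost wholly on assumed inputs, and that using all 50 patients for testing fits the Details section poorly.

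**Conclusion.** The point holds as an undefined counting unit and a missing rule for the primary outcome. Read in order, the steps lead most directly to image counts set against a patient-level reference. A table filled that way would not answer how often a patient is staged correctly.

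The loss of precision is conditional: it arises if images are counted, treated as independent and positively correlated within patients. Under the assumptions shown, an apparent ±2.5 points would stand where ±6.4 to ±10.0 is warranted for the same images, and ±11.1 when 50 patients are counted once.

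A reader might infer that the plan claims, or fails, its 5% precision. It does neither: it gives no interval, alpha or resulting sample size, and 5% is not defined as a half-width. Nor do the documents show that an image-level point estimate would be biased in a particular direction, and none is asserted here.

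**What to change.** - In Details and in Comparing AI success to pathology results, state that each patient counts once in the 5x5 table and in every sensitivity, specificity, predictive value and accuracy figure.
- State the output level of the algorithm. Fix the rule from image outputs to one T stage per patient, including which scan or scans it uses, on training patients and before test results are seen. The rule must also return a result for T0. Using more than one scan is compatible with counting a patient once.
- Base any interval on the number of test patients. Report image-level figures only as descriptive, with intervals clustered by patient.
- For pilot patients already evaluated, re-tabulate by patient and say that the rule was set afterwards.

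No new data are needed. The cost is some work to set the rule, a smaller reported N and wider intervals.

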### **Outcome measures:**

- 1- prediction of "T" stage: there are 5 stages

$T_0$  → sensitivity, specificity, accuracy

$T_1$  → sensitivity, specificity, accuracy

$T_2$  → sensitivity, specificity, accuracy

$T_3$  → sensitivity, specificity, accuracy

$T_4$  → sensitivity, specificity, accuracy

**Comparing AI success to pathology results:**

	PATHOLOGY T 0	PATHOLOGY T 1	PATHOLOGY T 2	PATHOLOGY T 3	PATHOLOGY T 4	TOTAL
AI-T0	A	B	C	D	E	A+B+C+D+E
AI-T1	F	G	H	I	J	F+G+H+I+J
AI-T2	K	L	M	N	O	K+L+M+N+O
AI-T3	P	Q	R	S	T	P+Q+R+S+T
AI-T4	U	V	W	X	Y	U+V+W+X+Y
TOTAL	A+F+K+P+U	B+G+L+Q+V	C+H+M+R+W	D+I+N+S+X	E+J+O+T+Y	A+B+C+...+X+Y

- Sensitivity of AI-T1 =  $\frac{G}{B+G+L+Q+V}$
- Accuracy of AI-T1 =  $\frac{G+(A+M+S+Y)}{A+B+C+\dots+X+Y}$ 
  - for us 5% prediction precision will be important
- Sample size formula =  $\frac{Z_{1-\alpha/2}^2 \times S_N \times (1-S_N)}{L^2 \times Prevalence}$

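### The accuracy formula printed for T1 is overall accuracy, identical for every stage, and the only sample size formula fits one stage's sensitivity and not the primary outcome

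*Combined protocol and SAP*

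**What the plan says.** Primary outcomes names "The accuracy of the algorithm developed with artificial intelligence" in predicting T stage. Outcome measures states that "there are 5 stages" and lists sensitivity, specificity and accuracy separately for each of T0 to T4.

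The section comparing AI success to pathology results sets out a five-by-five table with cells A to Y (AI in rows, pathology in columns) and works two measures for T1. Sensitivity is G over the T1 pathology column, B+G+L+Q+V. Accuracy is G+(A+M+S+Y) over the total. Below the accuracy formula stands the line "for us 5% prediction precision will be important". Then comes the "Sample size formula", Z² × S_N × (1−S_N) / (L² × Prevalence). S_N, L and Prevalence are not defined. No values are entered for them or for alpha, and no N is derived.

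On numbers, Duration of study/number of patients says "The current pilot study was evaluated with data from 50 patients", without reference to the formula. Design adds that "This research is the first pilot study of an ongoing project".

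**The concern.** There are two problems, and the first needs no assumption.

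- **Accuracy label.** The formula labelled as T1 accuracy adds up the whole diagonal, so it does not depend on the stage. An analyst who follows the section cannot deliver the five stage accuracies that Outcome measures asks for. The value reported under each stage's name would be something else.
- **Sizing.** A prevalence term belongs to a measure whose denominator is a subgroup, such as the sensitivity of one stage. The printed accuracy has all patients in its denominator and needs no such term. The only sizing rule in the plan therefore does not match the named primary outcome, and the 5% could be attached to either measure with very different N.

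At stake are the correctness of the stage accuracies and whether the number of test patients in the continuing project is set for the measure the sponsor cares about.

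**Working it through.** **1. Accuracy label** (cells from the plan's table)

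- Printed for T1: [G+(A+M+S+Y)]/total. The same pattern for T0 gives [A+(G+M+S+Y)]/total. These are the same five cells, and the same holds for T2 to T4.
- T1 versus rest: G (true positives) plus the 16 cells outside the T1 row (F to J) and the T1 column (B, G, L, Q, V), over the total.
- Four of those 16 cells are A, M, S and Y. The other 12 (C, D, E, K, N, O, P, R, T, U, W, X) are patients who were neither T1 nor called T1. For the question of T1 or not they are correct, but the printed formula counts them as errors. The printed value can therefore never exceed the stage-versus-rest value, and equals it only when all 12 cells are empty.
- Illustration (assumed): 50 patients, 10 per stage, 8 correct, and 2 wrong calls into each stage.
  - Printed: 5 × 8 = 40; 40/50 = 80% (exact 95% interval 66.3 to 90.0), for every stage.
  - Stage versus rest: TP 8, FN 2, FP 2, TN 50 − 12 = 38; 46/50 = 92% (80.8 to 97.8).
  - Check: there are 10 errors in all, of which 4 involve the stage; the other 6 make up the gap between 40 and 46.

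**2. Sample size formula**

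The plan states no N, so there is nothing to reproduce.

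- Printed: N_sens = Z² × S(1−S) / (L² × Prev).
- Overall accuracy: N_acc = Z² × Acc(1−Acc) / L².
- At the same assumed value, L and alpha, N_sens/N_acc = 1/Prev. Five stage shares sum to at most 1, so the smallest is at most 1/5 and the ratio is at least 5. Pathological evaluation also lists TX and Tis, which have no row in the table. Any such patients only lower the shares, so the bound stands.

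Assumptions for the figures: two-sided 95% (Z = 1.96) and 5% read as half-width (L = 0.05). The 0.55 is the lower end of the CT/MRI accuracy range in the Introduction; 0.80 and 0.90 are illustrative.

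| Assumed value | Overall accuracy | Printed formula, 20% prevalence |
|---|---|---|
| 0.55 | 381 | 1,902 |
| 0.80 | 246 | 1,230 |
| 0.90 | 139 | 692 |

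For example, at 0.90: 1.96² × 0.09 / 0.0025 = 138.3, so 139. Dividing 138.3 by 0.20 gives 691.5, so 692.

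**3. Direction**

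- Smallest stage, same value: with 692 test patients the half-width for overall accuracy is 1.96 × √(0.09/692) = 2.2 points at 0.90, and 1.96 × √(0.25/692) = 3.7 points at worst. Accuracy is oversized.
- Common stage, high assumed sensitivity: at 50% prevalence and S = 0.90 the printed formula gives 276.6, so 277. Accuracy at 0.55 needs 380.3, so 381. With 277 the half-width is 1.96 × √(0.2475/277) = 5.9 points. Accuracy is undersized.
- The factor of five needs equal assumed values. At 20% prevalence, accuracy 0.80 with sensitivity 0.90 gives a ratio of 2.81; accuracy 0.90 with sensitivity 0.80 gives 8.89.
- If 5% means full width (L = 0.025), the figures at 0.90 are 554 and 2,766. The ratio does not change.

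**The case against.** The strongest reply concerns the sizing point. Accuracy in Primary outcomes may be meant broadly, as diagnostic performance. Stage sensitivity is a listed outcome measure, so the formula would then size something the plan does want, and usually the more demanding quantity. The symbols are undefined, so reading S_N as stage sensitivity is an inference. Prevalence could even mean cancer among those enrolled. Under the Inclusion criteria that is 1, and the formula becomes the accuracy formula. Finally, this is a pilot, and too many patients would do the primary outcome no harm.

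Much of this stands. The plan does not say which reading is meant, the 692 exists only under assumed inputs, and in that example the effect is oversizing. What remains is that no reading makes the printed formula serve both measures. With Prevalence as a stage share it does not size overall accuracy, and with Prevalence equal to 1 it does not size any stage's sensitivity. Oversizing is also not guaranteed, as the 277 against 381 shows.

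None of this touches the accuracy label, which is wrong whatever the symbols mean.

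**Conclusion.** The label error is certain. The formula given for T1 accuracy is overall accuracy, the same for all five stages, and it understates stage-versus-rest accuracy whenever patients outside that stage are misplaced among the other stages (80% against 92% in the illustration).

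The sizing mismatch is real but secondary. On its natural reading the only sample size formula sizes one stage's sensitivity. At equal value, L and alpha it asks for at least five times the accuracy N for the smallest stage. That factor is algebra; every N above rests on the stated assumptions.

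Two stronger readings are not supported:

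- A reader might infer that the 50 patients miss a promised 5% precision. Nothing in the plan says the pilot is to deliver 5%. Design calls it a pilot of a wider project, and the title line above these formulas refers to the T "stage of esophageal and gastric cancers in computed tomography images", which is wider than the esophageal pilot. The 5% may belong to the continuing project.
- A reader might infer that the formula leaves the primary outcome short of patients, or that 692 is the plan's requirement. The plan enters no inputs and derives no N, and applied to the smallest stage at the same assumed value the formula gives more patients than accuracy needs.

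**What to change.** 1. Relabel (A+G+M+S+Y)/total as overall accuracy, and name it as the primary measure if that is what Primary outcomes means. Define stage accuracy as stage versus rest: for T1, G plus the 16 cells outside the T1 row and column, over the total, and likewise for the other stages.
2. Size overall accuracy with n = Z² × Acc × (1−Acc) / L² in independent test patients, without the prevalence term, and write in alpha, the assumed accuracy, L and N. Keep the printed formula only for stage sensitivity, naming the stage and its expected prevalence, or call stage results descriptive. Say whether the 5% applies to the pilot or to the continuing project. Because the pilot is described as already evaluated, date these decisions as made afterwards.
3. Report each measure with numerator, denominator and exact 95% interval.

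Cost: for the pilot, wording and re-tabulation of existing results, with no extra patients; the stage results from 50 patients become descriptive. For the continuing project, which "is planned to last two years", the N depends on which measure carries the 5%.
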